6.6. Planned Analyses

The following analyses will be conducted on cleaned data:

- 1. An IA of safety and immunogenicity data will be performed after all participants have completed Day 57 (28 days after the IP injection). Analysis of nAbs will include baseline, Day 29 and Day 57 visits; Analysis of other immunogenicity data will depend on data availability at the time of analysis. The IA will be performed by a separate team of unblinded programmers and statisticians. Pre-identified Sponsor team members will be unblinded to review treatment level results, as defined in the study Data Blinding Plan. The unblinded statistics team will not be involved in either study design or the regular study conduct. The participants and study sites will remain blinded until the conclusion of the study. The IA will serve as the basis for the progression to the ZIKV Phase 3 studies.
- 2. The final CSR will include full unblinded analyses of all safety and immunogenicity with individual unblinded listings through Day 196 (all data through approximately 6 months after the last IP injection). Note that safety data will be reported cumulatively up to the cutoff date, and immunogenicity data will be reported for each participant up to their Day 196 visits.

3. An addendum to the CSR will include the safety and immunogenicity data from Month 8 until EOS for all participants enrolled in the Extension Period.

In addition, unblinded data presentation or analysis for DSMB review will be handled by the unblinded team of statisticians and programmers, who are not involved in study design. More details regarding DSMB analysis can be found in the DSMB Charter.

7. Changes from Planned Analyses in Protocol

Not applicable.

8. References

Department of Health and Human Services (DHHS), Food and Drug Administration, Center for Biologics Evaluation and Research (US). Guidance for industry: Toxicity grading scale for healthy adult and adolescent volunteers enrolled in preventative vaccine clinical trials. September 2007 [cited 2019 Apr 10] [10 screens].

Available from:

https://www.fda.gov/downloads/BiologicsBloodVaccines/GuidanceComplianceRegulatory Information/Guidances/Vaccines/ucm091977.pdf.List of Appendices

9. List of Appendices

9.1. Appendix A Standards for Safety and Immunogenicity Variable Display in TFLs

Continuous Variables: The precision for continuous variables will be based on the precision of the data itself. The mean and median will be presented to one decimal place more than the original results; the SD will be presented to two decimal places more than the original results; the minimum and maximum will be presented to the same precision as the original results.

Categorical Variables: Percentages will be presented to 1 decimal place.

9.2. Appendix B Analysis Visit Windows for Safety and Immunogenicity Analysis

Safety and Immunogenicity Analysis will be summarized using the following analysis visit window for post injection assessments:

Step 1: If the safety and immunogenicity assessments are collected at scheduled visit, i.e. nominal scheduled visit, the data collected at scheduled visit will be used.

Step 2: If the safety and immunogenicity assessments are not collected at the scheduled visit, assessments collected at unscheduled visit will be used using the analysis visit windows described in Table 3 below.

If a subject has multiple assessments within the same analysis visit, the following rule will be used:

- If multiple assessments occur within a given analysis visit, the assessment closest to the target study day will be used.
- If there are 2 or more assessments equal distance to the target study day, the last assessment will be used.

Table 3 Visit Window

Visit	Target Study Day	Visit Window in Study Day
Vital Signs		
Day 1	1 (Date of First Injection)	≤1, Pre-first-dose

Day 1	1 (Date of First Injection)	1, Post-first-dose
Day 8	8	[2, 18]
Day 29	29 (Date of Second Injection)	[19, 29] Pre-second-dose
Day 29	29 (Date of Second Injection)	[29, 32] Post-second-dose
Day 36	36	[33, 46]
Day 57	57	[47, 71]
Day 85	85	[72, 140]
Day 196	196	[141, 280]
Day 364	364	[281, 448]
Day 532	532	[449, 616]
Day 700	700	[617, 760]
Antibody-Mediated Immur	nogenicity ¹	
Day 1	1 (Date of First Injection)	1, Pre-first-dose
Day 8	8	[2, 18]
Day 29	29	[19, 32]
Day 36	36	[33, 46]
Day 57	57	[47, 71]
Day 85	85	[72, 140]
Day 196	196	[141, 280]
Day 364	364	[281, 448]
Day 532	532	[449, 616]
Day 700	700	[617, 760]
Cell-Mediated		
Immunogenicity		
Day 1	1 (Date of First Injection)	1, Pre-first-dose
Day 29	29	[19, 32]
Day 36	36	[33, 46]
Day 57	57	[47, 126]
Day 196	196	[127, 280]
Day 364	364	[281, 448]

Day 532	532	[449, 616]
Day 700	700	[617, 760]

¹ NS-1 data collected prior to Day 85 will be mapped according to the visit window for available data.

9.3. Appendix A Imputation Rules for Missing Prior/Concomitant Medications and Non-Study Vaccinations

Imputation rules for missing or partial medication start/stop dates are defined below:

- 1. Missing or partial medication start date:
 - If only Day is missing, use the first day of the month, unless:
 - The medication end date is after the date of first injection or is missing AND the start month and year of the medication coincide with the start month and year of the first injection. In this case, use the date of first injection
 - If Day and Month are both missing, use the first day of the year, unless:
 - The medication end date is after the date of first injection or is missing AND the start year of the medication coincide with the start year of the first injection. In this case, use the date of first injection
 - If Day, Month and Year are all missing, the date will not be imputed, but the medication will be treated as though it began prior to the first injection for purposes of determining if status as prior or concomitant.
- 2. Missing or partial medication stop date:
 - If only Day is missing, use the earliest date of (last day of the month, study completion, discontinuation from the study, or death).
 - If Day and Month are both missing, use the earliest date of (last day of the year, study completion, discontinuation from the study, or death).
 - If Day, Month and Year are all missing, the date will not be imputed, but the medication will be flagged as a continuing medication.

In summary, the prior, concomitant or post categorization of a medication is described in Table 4 below.

Table 4. Prior, Concomitant, and Post Categorization of Medications and Non-study Vaccinations

	Medication Stop Date		
Medication Start Date	< First Injection Date of IP	≥ First Injection Date and ≤ 28 Days After Last Injection	> 28 Days After Last Injection [2]
< First injection date of IP [1]	P	P, C	P, C, A
\geq First injection date and \leq 28 days after last injection	-	C	C, A
> 28 days after last injection	-	-	A

A: Post; C: Concomitant; P: Prior

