1.3. Schedule of Assessments

The Schedules of Assessments for the Vaccination Period and the Extension Period are presented in Table 1 and Table 2, respectively.

If a participant cannot attend a study site visit (scheduled or unscheduled) with the exception of Day 0, Day 1, and Day 29 Visits, a home visit is acceptable if performed by appropriately delegated study site staff or a home healthcare service provided by the Sponsor. If neither a participant visit to the study site nor a home visit to the participant is possible (with the exception of Day 0, Day 1, and Day 29 Visits), a safety telephone call should be performed that includes the assessments scheduled for the safety telephone calls scheduled on Days 112 through 168 (Table 1).

Table 1: Schedule of Assessments for the Vaccination Period and for the Follow-Up Period (Approximately 6 Months)

Procedure	Eligibility		Vaccination Period Follow-Up Period					Unscheduled		
Study Day	D0 ¹ (Eligibility)	D1 ¹ (Baseline)	D8	D29	D36	D57	D85	D112, D140, D168	D196	
Visit Number	0	1	2	3	4	5	6	7-9	10 and EOS ²	Unscheduled
Type of Visit	C	C	C	C	C	C	C	SC	C	C
Window Allowance (Days)	-8		+3	-3/+7	+3	-3/+7	-3/+7	± 15	± 15	
Informed consent, inclusion and exclusion criteria, demography, prior and concomitant medications, and medical history	X									
Physical examination and vital sign measurements ³	X	X	(X)	X	(X)	X	(X)		(X)	(X)
Blood sample for baseline flavivirus serostatus assessments ^{4, 5}		X								

Procedure	Eligibility			Vaccination Per	riod			Follov Per		Unscheduled
Study Day	D0 ¹ (Eligibility)	D1 ¹ (Baseline)	D8	D29	D36	D57	D85	D112, D140, D168	D196	
Visit Number	0	1	2	3	4	5	6	7-9	10 and EOS ²	Unscheduled
Type of Visit	С	C	С	C	C	C	С	SC	C	C
Window Allowance (Days)	-8		+3	-3/+7	+3	-3/+7	-3/+7	± 15	± 15	
Blood sample for antibody-mediated immunogenicity ⁶		X	X	X	X	X ⁷	X		X	
PBMC collection for cellular immunity (subset of participants from approximately 4 selected sites)		X		X	X	X			X	
Pregnancy test ⁸	X	X		X						
Randomization		X								
IP injection (including 30-minute safety observation period after IP injection) ⁹		X		X						
Participant eDiary recording of solicited ARs (7 days)		X (Days 1-7)		X (Days 29-35)						
Participant eDiary recording of unresolved solicited ARs (up to 28 days)		X (Days 1-29 and Days 29-57)								
Review of eDiary			X		X					
Follow-up safety telephone call ¹⁰								X		
Recording of MAAEs		X	X	X	X	X	X	X	X	X
Recording of SAEs and AESIs		X	X	X	X	X	X	X	X	X

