4. STUDY DESIGN

4.1. General Design

This is a Phase 2, randomized, observer-blind, placebo-controlled, dose confirmation study.

All participants will be evaluated for their eligibility (Section 4.1.1) for enrollment in the Vaccination Period and will be followed for approximately 6 months (Day 196) after their last IP injection (Section 4.1.2). Table 1 displays the Schedule of Assessments (SOA) for all participants through Day 196. All participants in all treatment arms will have the opportunity to continue to be followed as part of an approximately 24-month Extension Period (through Day 700) after their last IP injection (Section 4.1.3). Table 2 displays the SOA for participants who continue into the Extension Period through Day 700. The study design is illustrated in Figure 1.

A total of approximately 800 participants will be randomly assigned to receive either µg or µg mRNA-1893 administered as a 2-dose regimen with at least a 28-day interval between vaccinations (Treatment Arm A or Treatment Arm B), or µg mRNA-1893 administered as a 1-dose regimen (Treatment Arm C), or placebo control administered as a 2-dose regimen with at least a 28-day interval between doses (Treatment Arm D) according to a 1:1:1:1 randomization ratio (ie, 200 participants per treatment arm with approximately 100 participants per baseline flavivirus serostatus in each treatment arm). Randomization was stratified by participants' baseline flavivirus serostatus assessed by a rapid dengue point-of-care test on site in the original protocol (dated 21 Feb 2021). Under the current protocol amendment, randomization will be stratified only by participants' region (continental US and Puerto Rico). All treatment arms will be enrolled in parallel. In order to maintain the blinding and to have the same study evaluation time point with both mRNA-1893 dose regimens relative to the last IP injection, participants randomly assigned to Treatment Arm C will be administered placebo at Day 1 and mRNA-1893 at Day 29 (Table 6).

Table 6: Treatment Arms

	Study Day	
	Day 1	Day 29
Treatment Arm A	mRNA-1893 μg First vaccination	mRNA-1893 μg Second vaccination
Treatment Arm B	mRNA-1893 μg First vaccination	mRNA-1893 μg Second vaccination
Treatment Arm C	Placebo	mRNA-1893 μg First vaccination
Treatment Arm D	Placebo	Placebo

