6.4. Investigational Product Compliance

All doses of IP will be administered at the study site under direct observation of unblinded pharmacy personnel and appropriately recorded (date and time) in the electronic case report forms (eCRFs). Unblinded pharmacy personnel will confirm that the participant has received the entire dose of IP. If a participant does not receive IP or does not receive all of the planned doses, the reason for the missed dose will be recorded.

Participants who miss the second vaccination due to noncompliance with the visit schedule will still be required to follow the original visit and testing schedule as described in the protocol. Unless consent is withdrawn, a participant who withdraws or is withheld from receiving the second dose of IP will remain in the study and complete all safety and immunogenicity assessments required through the scheduled EOS.

The study site is responsible for ensuring participants comply with the study windows allowed. If a participant misses a visit, every effort should be made to contact the participant and complete a visit within the defined time window (Table 1 and Table 2). If a participant does not complete a visit within the time window, that visit will be classified as a missed visit and the participant will continue with subsequent scheduled study visits. All safety requirements of the missed visit will be captured and included in the subsequent visit (eg, eDiary review for reactogenicity, immune testing, as applicable).

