5.5. Per-Protocol Sets

The Per-Protocol (PP) Set for Antibody-Mediated Immunogenicity

PP Set for Antibody-Mediated Immunogenicity consist of all FAS participants who

- a) comply with the vaccination schedule,
- b) comply with the timings of immunogenicity blood sampling to have post-vaccination results available for at least one assay component corresponding to the immunogenicity analysis objective (antibody-mediated immunogenicity endpoints), and
- c) have no major protocol deviations that impact immune response during the period corresponding to the immunogenicity analysis objective (antibody-mediated immunogenicity endpoints).

The PP Set for Antibody-Mediated Immunogenicity will serve as the primary population for the analysis of antibody-mediated immunogenicity data in this study. Participants will be included in the vaccination group to which they are randomized.

PP Set for CMI

PP Set for CMI consist of all FAS for Cell-Mediated participants who

- a) comply with the vaccination schedule,
- b) comply with the timings of immunogenicity blood sampling to have post-vaccination results available for at least one assay component corresponding to the immunogenicity analysis objective (CMI endpoints), and

c) have no major protocol deviations that impact immune response during the period corresponding to the immunogenicity analysis objective (CMI endpoints).

The PP Set for CMI will serve as the primary population for the analysis of CMI data in this study. Participants will be included in the vaccination group to which they are randomized.

Participants who did not take blood sample for immunogenicity within [21, 42] days after the second injection date will be excluded from the Per-Protocol Set. Participants who only received 1 dose or who received the second dose outside of the window [21, 42] will be excluded from the Per-Protocol Set.

6. Statistical Analysis

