6.1. General Considerations

The Schedule of Assessments is provided in Appendix E for the vaccination period and the follow-up period, and Appendix F for the extension period.

Continuous variables will be summarized using the following descriptive summary statistics: the number of subjects (n), mean, standard deviation (SD), median, minimum (min), and maximum (max).

Categorical variables will be summarized using counts and percentages.

Baseline value, unless specified otherwise, is defined as the most recent non-missing measurement (scheduled or unscheduled) collected before the first dose of IP. For immunogenicity tests, the baseline is defined as the most recent non-missing measurement (scheduled or unscheduled) collected before or on the date of first dose of IP.

For the summary statistics of all numerical variables unless otherwise specified, the display precision will follow programming standards. Please see Appendix A for variable display standards.

When count data are presented, the percentage will be suppressed when the count is zero in order to draw attention to the non-zero counts. A row denoted "Missing" will be included in count tabulations where specified on the shells to account for dropouts and missing values. The denominator for all percentages will be the number of subjects in that vaccination group within the analysis set of interest, unless otherwise specified.

Study day relative to the first injection will be calculated as below:

a) study day prior to the first injection will be calculated as: date of assessment/event
 date of the first injection;

b) study day on or after the date of the first injection will be calculated as: date of assessment/event – date of the first injection + 1;

Study day relative to the most recent injection will be calculated as below:

- a) study day prior to the first injection will be calculated as: date of assessment/event
 date of the first injection;
- b) study day on or after the date of the first injection but before the second injection (if applicable) will be calculated as: date of assessment/event date of the first injection + 1;
- c) study day on or after the date of the second injection will be calculated as: date of assessment/event – date of the second injection + 1; if study day is on the same day as the second injection, date and time will be compared with the second injection date and time.

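### SAP Table 3 places samples taken after dose 2 on a first-injection day scale, and no rule ties a Day 36 result to the actual time since dose 2

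*SAP*

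**What the plan says.** Protocol 4.1 explains that Arm C receives its active dose at Day 29 partly "to have the same study evaluation time point with both mRNA-1893 dose regimens relative to the last IP injection". The protocol describes Day 57 as 28 days after the last injection.

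Protocol Table 1 labels visits by study day and gives the allowances in one row: "Window Allowance (Days) -8 +3 -3/+7 +3 -3/+7 -3/+7 ± 15 ± 15". In visit order this is -3/+7 for Day 29, +3 for Day 36 and -3/+7 for Day 57. The table does not say whether visits after Day 29 move with the actual date of dose 2. Protocol 6.4 adds: "If a participant does not complete a visit within the time window, that visit will be classified as a missed visit". Section 4.1 separately requires a minimum of 28 days between vaccinations.

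SAP 6.1 defines two day counts. One is relative to the first injection: "study day on or after the date of the first injection will be calculated as: date of assessment/event" minus the first-injection date, plus 1. The other begins "Study day relative to the most recent injection will be calculated as below" and restarts at dose 2.

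SAP Appendix B opens with "Safety and Immunogenicity Analysis will be summarized using the following analysis visit window for post injection assessments". Under Step 1, for scheduled visits, "the data collected at scheduled visit will be used". Step 2 applies Table 3 to unscheduled assessments only. The antibody windows in Table 3 are Day 29 [19, 32], Day 36 [33, 46] and Day 57 [47, 71].

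SAP 5.5 requires an immunogenicity sample 21 to 42 days after the second-injection date for Per-Protocol membership, and adds: "Participants who only received 1 dose or who received the second dose outside of the window [21, 42] will be excluded from the Per-Protocol Set". It names neither the visit that the sampling rule refers to nor the origin of the dose window.

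**The concern.** The stated aim is evaluation at a fixed time after the last injection, but the rules that label a sample as Day 36 or later do not look at the second-injection date. A participant injected late within the allowance and one injected early can both contribute a Day 36 result at very different times after dose 2.

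Day 36 GMT, fold rise, ratio to placebo and seroconversion are secondary analyses (SAP 3.2 and 6.4.3). For Arm C, Day 36 is the first scheduled sample after its only active dose, and protocol 4.4 gives a rapid response as one reason for having that arm. Samples taken too soon after dose 2 to show a response would dilute these summaries.

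For Day 57 the concern is different. SAP 5.5 does count from dose 2, but its limits do not match Table 1, so following the schedule does not guarantee Per-Protocol membership.

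**Working it through.** **Inputs.** Table 1 allowances; SAP Table 3 windows; SAP 5.5 sampling limits of 21 to 42 days after dose 2; the 28-day minimum in protocol 4.1. Time since dose 2 = sample day minus dose 2 day.

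**1. The plan's own figures.** 57 - 29 = 28 days, as the protocol states; 36 - 29 = 7 days.

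**2. Which scale Table 3 uses.** Targets of 36 and 57 equal the nominal visit days counted from the first injection. On the most-recent-injection scale, the sample planned 7 days after dose 2 would be day 8. Table 3 is therefore on the first-injection scale, although it does not say so.

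**3. Table 1 windows if counted from Day 1 (assumption).** Dose 2: 29 - 3 = Day 26 to 29 + 7 = Day 36. Visit 4: Day 36 to 39. Visit 5: 57 - 3 = Day 54 to 57 + 7 = Day 64.

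| Reading | Day 36 sample, days after dose 2 | Day 57 sample, days after dose 2 |
|---|---|---|
| Table 1 from Day 1 | 36 - 36 = 0 to 39 - 26 = 13 | 54 - 36 = 18 to 64 - 26 = 38 |
| Same, dose 2 on or after Day 29 (28-day minimum) | 0 to 39 - 29 = 10 | 18 to 64 - 29 = 35 |
| First row with the SAP 5.5 sampling limits | no rule for this visit | 21 to 38 |
| Second row with the SAP 5.5 sampling limits | no rule for this visit | 21 to 35 |
| Same allowances counted from dose 2 | 7 to 10 | 28 - 3 = 25 to 28 + 7 = 35 |

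**4. In window but outside the Per-Protocol Set.** There are 11 dose days and 11 visit days, so 11 × 11 = 121 pairs. Those under 21 days are dose Day 34 with visit Day 54 (20 days), dose Day 35 with visit Day 54 or 55 (19, 20), and dose Day 36 with visit Day 54, 55 or 56 (18, 19, 20): 6 of 121. This counts calendar combinations and is not an estimated proportion of participants.

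No other scheduled sample rescues these participants. Visit 4 is at most 13 days after dose 2. Visit 6 (Day 85, -3/+7) opens on Day 82, and 82 - 36 = 46, which exceeds 42. This is also why I read the SAP 5.5 sampling rule as referring to Day 57.

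**5. The Day 29 / Day 36 boundary in Table 3.** The antibody Day 29 window ends at Day 32, while Table 1 allows that visit and injection until Day 36. An unscheduled sample taken on Days 33 to 36, before a late in-window dose 2, would therefore be classed as Day 36. With dose 2 on Days 26 to 36, the [33, 46] window spans 33 - 36 = -3 to 46 - 26 = 20 days after dose 2.

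**The case against.** The strongest reply is that the Day 1 anchor in Table 1 is an inference. Some text points the other way: Day 57 is described relative to the last injection, extension visits are counted from it, and Visit 4 has no minus allowance, which suits a completed 7-day diary. If sites schedule from dose 2, the ranges are 7 to 10 and 25 to 35 days. Table 3 would also hold those visits: Days 26 + 7 = 33 to 36 + 10 = 46 for Visit 4, and 26 + 25 = 51 to 36 + 35 = 71 for Visit 5. This stands as far as it goes, so the ranges must be stated conditionally. It does not settle the matter. The labels are study days, no sentence moves them, and Visit 4 held on Day 43 after a Day 36 injection would be a missed visit under protocol 6.4 if the windows count from Day 1. Table 3's limits also lie at the midpoints between target days, so the fit does not show intent.

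Other parts of the reply also stand:

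- The ranges come from Table 1. Table 3 governs unscheduled samples only.
- SAP 5.5 already controls the primary Day 57 analysis.
- The upper ends of 13 and 38 days require a dose 2 earlier than the 28-day minimum permits.
- There is no hypothesis testing, and the interim neutralising-antibody analysis uses baseline, Day 29 and Day 57 (SAP 6.6).
- Randomised, blinded arms should share much the same spread of timing.

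A reader might also infer that reactogenicity review is lost when Visit 4 comes early. Protocol 6.4 carries a missed visit's safety requirements, including diary review, to the next visit, and protocol 8.5.1 provides for later review of reactions lasting beyond Day 7. That inference is not supported.

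**Conclusion.** The point holds in a limited form. SAP Table 3 sits on a first-injection scale, and Step 1 accepts any nominal visit, so nothing in the analysis rules ties a Day 36 result to dose 2. If Table 1 counts from Day 1, an in-window Day 36 sample may be 0 to 13 days after dose 2, or 0 to 10 with the 28-day minimum enforced. For Day 57 the primary Per-Protocol range is 21 to 38 days. Samples at 18 to 20 days can remain only in the Full Analysis Set, which is supportive. On the same assumption, 6 of 121 in-window day pairs lead to Per-Protocol exclusion. The Day 29 / Day 36 boundary problem for unscheduled samples follows from Table 3 and the allowed injection days.

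Two stronger readings are not supported. One is that Day 36 titres are biased by a stated amount: the documents give neither the distribution of dose 2 dates nor the antibody rise in the first days after it, so no factor can be derived. The other is that the primary Day 57 result or the decision to proceed to Phase 3 is compromised: SAP 5.5 limits the former, and the interim neutralising-antibody analysis does not use Day 36. What remains is imprecise timing in secondary Day 36 summaries, a small avoidable loss from the Per-Protocol Set, and rules that disagree with one another.

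**What to change.** In SAP Appendix B:

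- For participants who received dose 2, define the Day 36 and later windows by days since the second injection, using the most-recent-injection study day in SAP 6.1. That variable counts the injection day as 1, so days since dose 2 equal its value minus 1. Keep the first-injection scale for participants with no second injection.
- Do not summarise as Day 36 any sample taken before dose 2.
- Apply a stated days-since-dose-2 check to samples from nominal Day 36 visits as well as unscheduled ones.

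In SAP 5.5, state which visit's sample the [21, 42] rule refers to and the origin of the [21, 42] dose window. Then reconcile Table 1 (its visit anchor and the -3/+7 allowance at Day 29), the 28-day minimum in the text, and the SAP 5.5 windows. The sponsor should decide which governs; this point proposes no dosing or visit schedule.

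The cost is SAP wording and a variable built from injection and sampling dates already recorded (protocol 6.4 and 8.3.1). A few samples would change visit or drop from the Day 36 summary. Any change to Table 1 itself would go through the amendment process in protocol 11.1.7, but the Appendix B change does not depend on it.
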